1. BACKGROUND AND RATIONALE

Respiratory symptoms such as cough, wheeze, and breathlessness are amongst the commonest reasons for presentation to healthcare in the United Kingdom, accounting for up to 22% of total patient contacts.(1) Chronic respiratory diseases also account for more than 10% of productive life lost secondary to medical issues, and are known to cause great detriment to the physical, psychological, and socioeconomic wellbeing of patients.(2-4) In recent years, the utility of macrolide antibiotics has been examined in a multitude of respiratory diseases. They are now recommended as add-on therapies in patients who continue to require regular treatment or hospitalisation for exacerbations of their chronic condition.(5)

The efficacy of macrolide antibiotics such as azithromycin in patients with asthma has been shown in large scale clinical trials. The AMAZES trial demonstrated a significant reduction in exacerbation frequency in those with persistent asthma, and both the AMAZES and AZISAST trials demonstrated an improvement in the quality of life in such patients. (6, 7) The reduction in exacerbation rates offered by azithromycin treatment is echoed in trials examining patients with COPD.(8, 9) Significant quality of life benefits, as measured by the SGRQ, were also observed in a pooled analysis of the trials examining COPD patients, but this did not reach the minimum clinically important difference of 4.(10) There is also high quality RCT evidence to support the use of long-term macrolides in patients with bronchiectasis, in the form of the EMBRACE, BAT, and BLESS trials. (11-13) Evidence for the use of long-term macrolides in other chronic respiratory diseases such as Interstitial Lung Diseases (ILD) and Chronic Cough (CC) is less clear, however this is largely due to the relative paucity of high-quality RCTs performed. There has been promising retrospective analysis performed on patients with Idiopathic Pulmonary Fibrosis (IPF). One trial demonstrated a reduction in hospital admissions and antibiotic courses prescribed for exacerbations of IPF, when comparing patients' records a year before treatment with the subsequent year where they were treated with azithromycin. (14) Two very small studies have examined the effect of long-term macrolides on CC, with only one trial measuring 24 hour cough counts in their analysis. (15, 16) However, other studies have shown benefit in cough-specific health status in other respiratory diseases. (17, 18) This suggests that the effect of long-term macrolides on patients with CC warrants further investigation with large-scale RCT, measuring their effect on both cough-specific QoL and 24-hour cough counts.

Despite the litary of evidence to support the use of long-term macrolide antibiotics in the management of respiratory disease, the mechanism of how they confer such a benefit to patients

remains obscure. One of the most popular proposed theories is that concerning the immunomodulatory effects of macrolides in the airways. (19, 20) Reduction of immune cell infiltration and neutrophil chemotaxis in the airways has been shown in vitro with erythromycin(21) and in vivo via the measurement of sputum interleukin-8 levels of asthmatic patients after treatment with clarithromycin. (22) Effects of macrolides on the function of innate immune cells have also been described, such as increasing the phagocytic capacity of macrophages(23) and promoting neutrophil apoptosis and therefore reducing airway inflammation. (24) Despite extensive study, there is still reasonable doubt that immunomodulatory properties are the sole mechanism for the beneficial effects of long-term macrolides. An alternative, more traditional, proposed mechanism is that of the antimicrobial effects of long-term macrolides on the airway. It is thought that macrolides may inhibit bacterial protein synthesis, toxin production, and biofilm function in respiratory disease where colonisation of common pathogenic bacteria is common.(25) Furthermore, long-term treatment with macrolides has been shown to alter the airway microbiota of patients with bronchiectasis, conveying their antibacterial effects. (26) Despite much research around these two processes, the pro-kinetic effects of long-term macrolides on the gastrointestinal system in relation to patients with chronic respiratory disease has been scarcely studied.

Macrolide antibiotics, such as azithromycin, have been shown to promote gastrointestinal motility and reduce the rates of gastro-oesophageal reflux events in patients with gastro-oesophageal reflux disease (GORD).(27, 28) Indeed, erythromycin has been used to promote gastric motility for patients in the intensive care unit for many years.(29, 30) This effect is engendered by agonism of the motilin receptor that macrolides such as erythromycin exhibit.(31) The link between gastrointestinal dysmotility and respiratory disease is well established, with both acidic GORD and non-acid gaseous airway reflux mechanisms implicated in the natural history of many chronic respiratory diseases.(32-36) Indeed, in our retrospective analysis of 441 patients with chronic respiratory disease and symptoms suggestive of airway reflux it was revealed that 66% of patients had evidence of oesophageal dysmotility, proven on High-Resolution Oesophageal Manometry (HROM).

Despite the evidence that gastrointestinal dysmotility is implicated in the natural history of respiratory disease and the fact that macrolides improve motility, there have been no studies investigating the effect of macrolides on oesophageal motility in this cohort of patients. We believe it important to perform a trial examining the effect of azithromycin, the most frequently used long-term macrolide, on oesophageal motility in patients with chronic respiratory disease. We will also investigate the relationship between the effect of oesophageal function and on symptom burden in this group of patients.

2. TRIAL AIMS AND OBJECTIVES

Aim: To investigate the feasibility and acceptability of HROM in the diagnosis and treatment strategies of chronic respiratory diseases. Exploratory analysis will be performed on the effect of azithromycin on oesophageal motility and how it relates to symptomatic improvement in patients with chronic respiratory disease who are being commenced on azithromycin as part of routine clinical care.

Objectives: Specific trial objectives will address both the feasibility and acceptability outcomes as well as exploratory outcomes.

Feasibility outcomes

- 1. Recruitment: eligibility to consent ratio, recruitment rate, and participant retention to follow-up.
- 2. Data quality: Completion of clinical outcomes at follow-up and patterns of missing data for the trial measures. Completion of participant symptom questionnaires throughout the study. Completion of trial processes, principally HROM.
- 3. Acceptability of assessment: Quantify the proportion of participants who judge the trial investigations, principally HROM, to be acceptable.

Exploratory clinical outcomes

- Oesophageal function: To evaluate the effect of azithromycin on oesophageal contraction vigour and swallow coordination. This will be evaluated by investigating participants with HROM before and 1 month after initiation of azithromycin as part of routine clinical care.
- Symptom burden: Symptoms will be assessed before and 1 month after initiation of azithromycin as part of routine clinical care. Symptoms will be measured using validated symptom questionnaires, visual analogue scale for cough, and numeric rating scales for breathlessness
- 3. Relationship between oesophageal motility and symptoms: The change in oesophageal functioning and presence of respiratory symptoms will be examined in each participant. The relationship between these two parameters will then be examined using statistical analysis.

4. Effect of azithromycin therapy on continuous objective cough frequency as measured by the Hyfe Cough Tracker©.

3. TRIAL DESIGN

A prospective observational trial evaluating the effect of 1 month (up to 6 weeks) of azithromycin treatment on oesophageal motility and symptom burden in patients with chronic respiratory disease who are being commenced on azithromycin as part of routine clinical care. Participants will be investigated using HROM before and during treatment with azithromycin to evaluate the change in oesophageal function.

The trial team will not be prescribing the azithromycin treatment for the participants, as this will be the decision and the responsibility of their usual treating clinician. However, it is anticipated that all participants will be treated with azithromycin 250 milligrams once daily or three times per week throughout the duration of the study. The acceptability of HROM as a diagnostic tool will be assessed through participant experience surveys. We will also analyse other feasibility outcomes such as eligibility to recruitment ratio and participant retention rate to ascertain how willing participants will be to engage in all trial procedures to inform larger clinical trials/ mechanistic studies.

Participants will be investigated with validated questionnaires to ascertain their symptom burden before and during treatment with azithromycin. With this information we will correlate changes in oesophageal function and symptom burden in this group of patients. Participants will also be asked to use the Hyfe Cough Tracker© equipment (to be further determined - if a dedicated smartphone running the application or a wearable smartwatch running the application) for at least one week prior to their initiation of azithromycin and for the duration of their azithromycin treatment whilst in the trial. We will then observe the difference between daily cough counts before and after azithromycin treatment and be able to ascertain how this correlates with oesophageal function. Additionally, we will look into the relationship of objective cough frequency data and repetitive subjective cough evaluation using cough VAS.

4. TRIAL POPULATION

Participants will be identified by their usual clinical team treating their chronic respiratory disease in secondary care outpatient services. Potential participants who are being considered for treatment with long-term azithromycin (defined as >6 months daily or three times weekly

treatment) will be alerted to the trial team and will be approached for potential participants in the study. All staff working within the study, including clinicians and specialist nurses, will undergo training in the trial protocol, including the inclusion and exclusion criteria.

For this study, all patients with a chronic respiratory disease, as diagnosed by a consultant respiratory medicine physician, who are being considered for long-term azithromycin therapy will be eligible for participation in the study.

Participants that do not meet all the inclusion criteria or who meet any of the exclusion criteria will be ineligible to participate in this study.

4.1 Inclusion Criteria

- Males and females aged ≥18 years.
- Have a diagnosis of chronic respiratory disease (COPD, asthma, interstitial lung disease, chronic cough, cystic fibrosis, and/or bronchiectasis) confirmed by a consultant respiratory physician.
- Exhibit symptoms consistent with airway reflux, demonstrated by a score ≥14 on the Hull Airways
 Reflux Questionnaire.
- Are being initiated on azithromycin treatment as part of routine clinical care by their usual clinician. This will include all common treatment regimes, 250mg once daily, 250mg three times per week, and 500mg three time per week.
- Are willing and able to consent to all trial procedures.

4.2 Exclusion Criteria

- Previous treatment with long-term macrolides in the past 3 months.
- Unable to be investigated with HROM due to contraindications such as anatomical abnormalities or diseases of the oesophagus or unwilling/ unable to be investigated with HROM based on the clinical judgement of the investigators due to severity of lung disease.
- Have another cardiorespiratory cause for their symptoms (such as heart failure or lung cancer).
- Are unable or unwilling to consent to or complete the trial procedures
- Women of child bearing potential not using effective means of contraception. Effective methods
 of contraception include any oral contraceptive pill, any intrauterine device, any long term
 contraceptive implant, and any long-acting contraceptive injection
- Have been involved in another medicinal trial (CTIMP) within past four weeks.

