6. OUTCOMES AND MEASURES

6.1 Feasibility outcomes

This study's primary outcomes will be the feasibility and acceptability outcomes, these include:

- Recruitment: eligibility to consent ratio, recruitment rate, and participant retention to followup.
- Data quality: Completion of clinical outcomes at follow-up and patterns of missing data for the trial measures. Completion of participant symptom questionnaires throughout the study. Completion of trial processes, principally HROM.
- Acceptability of assessment: Quantify the proportion of participants who judge the trial investigations, principally HROM, to be acceptable.

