7.2 Screening for Eligibility

A Participant Screening Log will be kept of all potentially eligible participants including the reasons for non-entry and/or non-approach, if applicable by all the study team.

An initial screening assessment will be undertaken prior to signing the informed consent form to ascertain that the participant may be potentially suitable for the trial and can be approached. Only eligible, consenting participants will proceed to undertake trial measures as outlined in Section 7.3.

The plan of management will be checked with the potential participant's usual treating physician to identify any planned or expected change to management during the trial period that may impact trial participation.

Participants identified as being potentially suitable for entry into the trial and who are approached about the trial and have given consent will undergo a review of eligibility criteria and complete eligibility screening.

Information about eligibility will be obtained from discussion with the potential participant and review of the participant's medical record.

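### HROM completion and acceptability are measured only in enrolled patients, while patients who cannot or will not have HROM are removed as ineligible and count in no HROM outcome

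*Protocol*

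**What the plan says.** Protocol Section 2 states the aim broadly: "To investigate the feasibility and acceptability of HROM in the diagnosis and treatment strategies of chronic respiratory diseases". It is not limited to patients already thought fit for the test.

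Section 6.1 gives these outcomes primary status: "This study's primary outcomes will be the feasibility and acceptability outcomes, these include" recruitment, data quality and acceptability. Two items concern HROM directly. Under data quality there is "Completion of trial processes, principally HROM", with no denominator stated. Under acceptability the task is: "Quantify the proportion of participants who judge the trial investigations, principally HROM, to be acceptable". Section 11 again lists acceptability of HROM among the primary feasibility outcomes.

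Section 4.2 excludes three relevant groups:
- contraindication: "Unable to be investigated with HROM due to contraindications such as anatomical abnormalities or diseases of the oesophagus";
- lung severity: patients unwilling or "unable to be investigated with HROM based on the clinical judgement of the investigators due to severity of lung disease";
- a general criterion: "Are unable or unwilling to consent to or complete the trial procedures".

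Section 4 makes anyone who meets an exclusion criterion ineligible.

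Two provisions touch the excluded patients. Section 7.2 says "A Participant Screening Log will be kept of all potentially eligible participants including the reasons for non-entry" and also asks for reasons for non-approach. Section 11 reports the eligibility and consent rates with 95% confidence intervals.

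**The concern.** When the question is whether HROM can be done in chronic respiratory disease, a patient who cannot have it, or refuses it, is direct evidence on that question. Under Section 4.2 that patient leaves before any HROM outcome is measured. Completion and acceptability are then observed in a group already filtered on ability and willingness to have the test, so both are selected towards success. The severity limb has no threshold, so the strength of the filter depends on individual judgement.

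The consent measure is exposed as well. A patient who declines because of HROM can be recorded as ineligible, and so drops out of the eligibility-to-consent ratio instead of counting as non-consent.

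Section 3 says the feasibility results are meant to inform larger trials and mechanistic studies. An enrolled-only HROM figure read as the figure for the disease population would carry the selection into that planning.

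**Working it through.** **Inputs.** The protocol gives no target completion rate, no expected number of HROM-related exclusions and no formal sample size calculation. There is therefore no stated figure to reproduce. From the protocol: N = 30 (Synopsis). Assumed: the number x of the 30 who complete baseline HROM, and q, the share of otherwise suitable patients not entered for an HROM reason, taken over 5% to 30%.

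**Step 1: does any stated outcome count these patients?**
- HROM completion (6.1): no denominator is given, but patients excluded under 4.2 are not in the study, so only enrolled patients can contribute.
- HROM acceptability (6.1): the denominator is participants, so no.
- Eligibility-to-consent ratio (6.1): it starts from eligible patients, so no. With C consenting, E classed eligible and R refusing because of HROM, classing the R patients as ineligible gives C/E, whereas counting them as non-consent gives C/(E + R), which is smaller whenever R > 0.
- Eligibility rate (Section 11): it can include them, but pooled with HARQ below 14, recent macrolides, contraception, participation in another trial and the rest.
- Screening log (7.2): it can record them, but covers only potentially eligible patients and is tied to no HROM outcome. Section 4.3 has clinicians refer patients who may meet the criteria, so someone plainly unable to have HROM may never reach the log.

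Selection is reinforced by Section 7.1, which admits patients who already had HROM within the previous 3 months and so have already shown they can have it.

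**Step 2: size as a function of q.** If m patients are not entered for HROM reasons, q = m/(30 + m). Enrolled-only completion is x/30. With the m patients in the denominator it is x/(30 + m) = (x/30)(1 - q). The ratio of the two is 1/(1 - q), whatever x is.

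| Assumed q | 1/(1 - q) | x = 27: 90% becomes | x = 30: 100% becomes |
|---|---|---|---|
| 5% | 1.05 | 0.90 × 0.95 = 85.5% | 95% |
| 10% | 1.11 | 0.90 × 0.90 = 81% | 90% |
| 20% | 1.25 | 0.90 × 0.80 = 72% | 80% |
| 30% | 1.43 | 0.90 × 0.70 = 63% | 70% |

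**Step 3: precision.** Exact (Clopper-Pearson) 95% intervals: 27/30 is 73.5% to 97.9%, and 30/30 is 88.4% to 100%. At q = 10%, m = 30 × 0.10/0.90 = 3.3, about 3, so 27/33 = 81.8% (64.5% to 93.0%). At q = 30%, m = 30 × 0.30/0.70 = 12.9, about 13, so 27/43 = 62.8% (46.7% to 77.0%). These intervals are wide and overlap that for 27/30. The difference is one of population, however, and sampling error does not account for it.

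**Step 4: can the wider denominator be built?** Not as all patients who meet every other criterion. HARQ is taken at the screening visit together with consent (7.3), and Section 13.2 puts consent before any study-specific procedure. Section 7.2 has an initial screen before consent, at which a known contraindication or severe disease could already stop approach. HARQ will then often be unknown. A workable denominator must accept no other known exclusion and treat HARQ as unknown where it was not taken. It should also use baseline HROM: under Section 4.4 patients who stop azithromycin do not repeat HROM, which says nothing about feasibility.

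**The case against.** The best defence has four parts.

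First, excluding patients who cannot safely have a procedure is ordinary practice. That stands, and the exclusion is not the fault; the gap lies in what is counted.

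Second, the information is largely collected: the log records reasons, the eligibility rate has an interval, and Section 7.4 offers the invitation survey to everyone screened, whether or not they consent. Tabulating reasons could be left to an analysis plan. This softens the point considerably. It does not close it, because the scope of the log is set in the protocol and an analysis plan cannot recover a reason that was never captured at screening.

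Third, HROM completion sits under data quality, where enrolled participants are the natural denominator, and a later trial with the same exclusion could plan from the eligibility rate and enrolled completion together. For such a trial that is fair. It does not answer the aim in Section 2, which is wider.

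Fourth, every exclusion count is an assumption. That is correct, and q may be small.

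A reader might infer that completion will be high almost by construction. The protocol does not support this. Enrolled patients can still fail to tolerate the catheter or to finish the swallows in Section 5.3, and Section 4.4 expressly foresees refusal of the second HROM. A reader might also take the severity clause as clinician-judged inability alone, with no bearing on consent. The clause names unwillingness too, so the consent ratio is affected.

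**Conclusion.** The point holds in a limited form. Followed as written, the HROM-specific primary figures describe patients already selected as able and willing to have HROM. Those excluded for HROM reasons enter no HROM outcome, and HROM refusal can be moved from non-consent to ineligibility. This concerns completion, acceptability and the eligibility-to-consent ratio; it does not extend to every recruitment measure.

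The overstatement of completion is a factor 1/(1 - q), from 1.05 to 1.43 over an assumed q of 5% to 30%. The protocol gives no basis for choosing within that range, so no particular overestimate, whether overall or for severe COPD or ILD, can be claimed. The factor rests on counting each HROM-related non-entry as not feasible and on leaving patients who decline for other reasons outside the denominator.

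**What to change.** Leave the safety exclusion in 4.2 unchanged.

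- **Section 7.2:** log every patient considered for long-term azithromycin who is not entered for an HROM reason, coded as contraindication, judged too severe, or unwilling to have HROM.
- **Section 6.1 and Section 11:** beside the enrolled-only figure, report a baseline HROM feasibility proportion with a 95% CI. The denominator is enrolled patients plus logged patients not entered for an HROM reason and with no other known exclusion, HARQ being treated as unknown where it was not taken.
- **Presentation:** show each HROM reason, and attempted but not completed, separately. Show patients who declined the trial for non-HROM reasons separately and outside the denominator.
- **Eligibility-to-consent ratio:** count HROM refusals as non-consent.
- **By diagnosis:** counts only, since about 30 participants over six listed diagnoses will not support useful intervals.

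The cost is slightly more logging, a denominator that is only approximate, and a less favourable feasibility figure. The log codes are best in place before recruitment starts, or as early in it as possible, because reasons not recorded at the time may not be recoverable.

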4.3 Participant Identification and Screening

All patients attending the Hull University Teaching Hospitals NHS Trust (HUTH) respiratory medicine outpatient department for management of their chronic respiratory disease and are being considered for long-term treatment with azithromycin will be considered suitable for participation. Respiratory medicine clinicians and specialist nurses working within the trust will be trained and instructed in the recruitment procedure and any patients who may meet the eligibility criteria will be referred to the trial team and contacted, with the patients' consent and after given time to consider participation and ask questions, for screening to assess eligibility to participate in the study.

Participants expressing an interest in the trial will be provided with a participant information sheet and informed consent will be obtained. All eligible patients who are approached for the trial will be invited to complete a short anonymous questionnaire (Appendix: Trial Invitation Experience Survey) assessing their experience of recruitment and why they consented to participate or declined.

Participants that fail screening can be re-screened (to a maximum of 3 times) if the reason for screen failure is resolved prior to completion of trial recruitment. Participants entering the trial following re-screening after an earlier failed screening will be allocated a new trial ID and have their earlier trial ID and the reason for initial screen failure recorded in their CRF and the Participant Master Index.

